7.2.2. Annualized Relapse Rate in the 205MS203-303 ITT Population

The annualized relapse rate will be summarized for the 205MS203-303 ITT population in the 205MS303 Treatment period. The relapse rate will be reported using relapses that occurred on or after the first DAC HYP dose date in the 205MS303 Treatment period. Relapses that occur after subjects receive alternative MS medications will be excluded from the analyses of relapse rate, and the subject’s time on study will be censored at the time the alternative MS medication is added.

The unadjusted ARR will be calculated as the total number of relapses experienced during the given period, divided by the total number of days in the period or the time of censoring, and the ratio then multiplied by 365.25. Relapse rate will be tabulated for all subjects combined.

For the 205MS303 Treatment period, the relapse rate will also be estimated using a negative binomial model, with adjustment for the number of relapses in a year prior to the first dose in 205MS303. The logarithmic transformation of the number of days in the study will be included in the model as the “offset” parameter. If the data are under-dispersed (assessed using the Pearson Chi-Squared statistic) or if the negative binomial model does not converge, a Poisson regression model will be used instead. The Poisson model will be adjusted for over-dispersion using a Pearson scale parameter.

To further assess the durability of treatment, the relapse rate will also be summarized by 48-week time intervals defined in the 205MS303 Treatment Period. For these analyses, rates will be tabulated by evaluating the number of relapses in each time interval and the amount of follow-up time in the time interval. A Poisson model will be used to estimate the relapse rate in each time interval unless data are over-dispersed in which case a negative binomial model will be used.

	Protocol 205MS303 Statistical Analysis Plan	Final Version 1.0
---	--	--------------------------

7.2.3. Annualized Relapse Rate in the 205MS302-303 ITT Population

The annualized relapse rate will be summarized for the 205MS302-303 ITT population in the 205MS303 Treatment Period. The relapse rate will be reported using relapses that occurred on or after the first dose date during the 205MS303 Treatment period. Relapses that occur after subjects receive alternative MS medications will be excluded from the analyses of relapse rate, and the subject's time on study will be censored at the time the alternative MS medication is added.

The unadjusted ARR will be calculated as the total number of relapses experienced during the given period, divided by the total number of days in the study period or the time of censoring, and the ratio then multiplied by 365.25.

The relapse rate may also be estimated using a negative binomial model, with adjustment for the number of relapses in a year prior to the first dose in 205MS303. The logarithmic transformation of the number of days in the study will be included in the model as the "offset" parameter. If the data are under-dispersed (assessed using the Pearson Chi-Squared statistic) or if the negative binomial model does not converge, a Poisson regression model will be used instead. The Poisson model will be adjusted for over-dispersion using a Pearson scale parameter.

To further assess the durability of treatment, the relapse rate may also be summarized by 48-week intervals in the 205MS303 Treatment Period. For these analyses, rates will be tabulated by evaluating the number of relapses in each time interval and the amount of follow-up time in the time interval. A Poisson model will be used to estimate the relapse rate in each time interval unless data are over-dispersed in which case a negative binomial model will be used.

7.3. Proportion of Subjects who Relapsed

7.3.1. Proportion of Subjects with Relapse in the 205MS301-303 ITT Population

The proportion of subjects who relapsed will be summarized using the following study population and study periods

- 205MS301-303 ITT population in the combined study period
- 205MS301-303 ITT population in the 205MS303 Treatment period

Relapse will be defined using the same definition that was used for the annualized relapse rate endpoint. The proportion of subjects who relapsed at selected time points, by treatment group of the 205MS301 study, will be estimated.

Kaplan-Meier curve of time to the first relapse during the study period (i.e., the Kaplan-Meier product-limit estimator) will be used to estimate the proportion of subjects who relapsed. If there are no early withdrawals, the Kaplan-Meier estimate of the proportion of subjects relapsed is same as the observed proportion of subjects relapsed. If there are early withdrawals, the Kaplan-Meier estimate has the advantage of taking into account the length of follow-up for the early withdrawals, without having any assumptions about whether those subjects relapsed or not.

Subjects without a confirmed relapse will be censored at either early withdrawal or the end of the corresponding study period. If a subject took an alternative MS medication before the first relapse, the subject will be censored at the time of the alternative MS medication. Kaplan-Meier plots of the

	Protocol 205MS303 Statistical Analysis Plan	Final Version 1.0
---	--	--------------------------

time to first relapse will also be presented and used to estimate the median time (and/or the 25th percentile) by the previous treatment group of the 205MS301 study.

7.3.2. Proportion of Subjects with Relapse in the 205MS203-303 ITT Population

The proportion of subjects who relapsed will be summarized for the 205MS203-303 ITT population in the 205MS303 Treatment period. Relapse will be defined using the same definition that was used for the annualized relapse rate endpoint. The proportion of subjects who relapsed at selected time points will be estimated and presented for all subjects combined. Kaplan-Meier curve of time to the first relapse during the study period will be used to estimate the proportion of subjects who relapsed.

Subjects without a confirmed relapse will be censored at either early withdrawal or the end of the 205MS303 Treatment period. If a subject took an alternative MS medication before the first relapse, the subject will be censored at the time of the alternative MS medication. Kaplan-Meier plots of the time to first relapse will also be presented and used to estimate the median time (and/or the 25th percentile) for all subjects combined.

7.3.3. Proportion of Subjects with Relapse in the 205MS302-303 ITT Population

The proportion of subjects who relapsed will be summarized for the 205MS302-303 ITT population in the 205MS303 Treatment period. Relapse will be defined using the same definition that was used for the annualized relapse rate endpoint. The proportion of subjects who relapsed at selected time points will be estimated. Kaplan-Meier curve of time to the first relapse during the study period will be used to estimate the proportion of subjects who relapsed. Subjects without a confirmed relapse will be censored at either early withdrawal or the end of the 205MS303 treatment period. If a subject took an alternative MS medication before the first relapse, the subject will be censored at the time of the alternative MS medication. Kaplan-Meier plots of the time to first relapse will also be presented and used to estimate the median time (and/or the 25th percentile).

7.4. Sustained 6-month Disability Progression

7.4.1. Sustained 6-month Disability Progression in the 205MS301-303 ITT Population

Time to confirmed 6-month disability progression will be summarized for the following populations and study periods:

- 205MS301-303 ITT population during the 205MS303 Treatment Period, from the date of first dose in 205MS303
- 205MS301-303 ITT population during the Combined Study Period, from the date of first dose in 205MS301

Sustained disability progression is defined as: at least a 1.0 point increase on the EDSS from baseline EDSS ≥ 1.0 that is sustained for 24 weeks, or at least a 1.5 point increase on the EDSS from

	Protocol 205MS303 Statistical Analysis Plan	Final Version 1.0
---	--	--------------------------

baseline EDSS = 0 that is sustained for 24 weeks. The date of the initial visit at which the minimum increase in the EDSS is met will be the date of onset of the progression. The EDSS progression is defined as confirmed when this minimum EDSS change is present on the next study visit occurring after 158 days from the initial observation.

For the Combined Study Period, progression will be calculated relative to the EDSS score at the 205MS301 baseline. For the 205MS303 Treatment Period, progression must start after the first dose in the 205MS303 study and will be calculated relative to 205MS303 baseline.

Progression will not be confirmed at a visit where a relapse is also occurring. A subject is considered to be having a relapse for at least 29 days after the start date of a protocol-defined relapse in 205MS301 or 205MS303. If a subject meets the defined criteria of sustained progression and is also having a relapse, the subject will be required to meet the defined minimum criteria at the subsequent visit.

If a subject had a tentative progression prior to the start of alternative MS medication, the appropriate EDSS evaluation performed while taking alternative MS medication will be used to assess confirmation of the progression. Death due to MS will be counted as progression. If the subject was in the midst of a tentative progression at the time of death (e.g. the EDSS evaluation prior to death is a tentative progression), the progression date will be the tentative progression start date. Otherwise, the progression date will be the date of death. If the death was not due to MS, then the subject will be censored using the same rules as for subjects who withdraw from the study.

Subjects who do not have a sustained progression based on the above rules (and have sufficient follow up data to confirm that there is no progression) will be censored. For the analyses based on either 205MS303 treatment period or the combined study period data, the censoring date will be the date of the last EDSS prior to the end date of the 205MS303 treatment period. Subjects who withdraw from the study after the baseline visit but prior to the first clinical evaluation scheduled visit will be censored at baseline.

For subjects with a tentative progression that cannot be confirmed because there are no additional EDSS assessments, the follow-up ends before a sustained progression occurs (i.e., due to the subject withdrawing from the study or due to the cutoff of data collection), or because the confirmatory assessment does not meet other criteria (i.e., the last EDSS assessment is <158 days after the tentative progression or the last EDSS assessment is at the time of a relapse), the censor date will be the date of the last EDSS assessment.

Time to confirmed disability progression will be explored using Kaplan-Meier method, with the first dose date in the corresponding study period as the start date, by the treatment group of the 205MS301 study. Kaplan-Meier method for time to disability progression will be used to estimate the proportion of subjects who experienced progression at selected time points, by treatment group of the 205MS301 study. A subject with sustained disability progression during the 205MS301 Treatment Period will still be considered at risk in the analysis for the 205MS303 Treatment Period.

Kaplan-Meier plots of the time to first progression will be presented and used to estimate the median time (and/or 25th percentile) by the previous treatment group of the 205MS301 study for each study period.

	Protocol 205MS303 Statistical Analysis Plan	Final Version 1.0
---	--	--------------------------

If the EDSS score is missing at the 205MS301 baseline visit, the 205MS301 screening score will be used instead for the 205MS301 baseline. If both baseline and screening scores are missing, the first available assessment will be used as the baseline EDSS score. For the 205MS303 baseline, the last available EDSS score before or on the first dose in the 205MS303 study will be used. The start date for calculation of day to progression or censoring will be the first dosing date in the corresponding period.

Imputation of subjects with tentative progression at their last assessment for (sensitivity analysis)

If a subject has a tentative progression at the last EDSS assessment and no EDSS assessments to confirm progression, the presence or absence of sustained disability progression will be imputed using a Multiple Imputation (MI) approach for the sensitivity analysis. Among subjects with at least one tentative progression, the probability of confirmation for those with a missing EDSS to confirm progression will be estimated via logistic model adjusting for treatment group of the 205MS301 study, EDSS at baseline (as a continuous variable), change in EDSS from baseline to the tentative progression and presence (or absence) of a relapse within the last 29-days of the tentative progression. For the subjects with multiple tentative progressions, the confirmed (if subject had a confirmed progression) or the last (if subject did not have any tentative progressions confirmed) tentative progression record will be retained. Based on these probability estimates, confirmed progression flags will be imputed via multiple imputations. The multiple imputations via this logistic regression model will be conducted 50 times with pre-specified random seed to generate 50 analysis datasets. Analyses will be conducted on each of the 50 data sets. Results will be combined to provide the final analysis results.

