5.2. Analysis of baseline data

The definition of baseline will be dependent on the analysis performed and the cohort of patients utilized. The following are the various definitions of baseline that may be used in the analyses:

5.2.1. 205MS301-205MS303 Study Baselines

205MS301 Baseline

Study 205MS301 Baseline is defined as the latest available value prior to or on the date of the first dose of study treatment in Study 205MS301.

205MS303 Baseline

Study 205MS303 Baseline is defined as the latest available value prior to or on the date of the first dose of study treatment in Study 205MS303.

Demographic characteristics, baseline disease characteristics and medical history will be summarized using the 205MS301-303 ITT population at the 205MS301 Baseline and at the 205MS303 Baseline.

DAC HYP Baseline

DAC HYP Baseline is equal to the 205MS301 baseline for subjects randomized to DAC HYP in 205MS301, or the 205MS303 baseline for subjects randomized to IFN β -1a in 205MS301. If no assessments, or if multiple measurements were performed on the day of first dose of DAC HYP, the last measurement prior to the first dose of DAC HYP will be used.

Unless otherwise specified, the DAC HYP Baseline will be utilized in measurements for safety assessments such as laboratory values and vital signs.

5.2.2. 205MS203-205MS303 Study Baselines

205MS303 Baseline is defined as the latest available value prior to or on the date of the first dose of study treatment in Study 205MS303.

DAC HYP Baseline

Subjects enrolled from 205MS203 study had completed the 205MS201, 205MS202, and 205MS203 studies. For subjects randomized to DAC HYP either 150 mg or 300 mg in 205MS201, the DAC HYP Baseline is defined as the 205MS201 baseline. For subjects randomized to placebo in 205MS201, the DAC HYP Baseline is defined as the 205MS202 Baseline. If no assessments, or if multiple measurements were performed on the day of first dose of DAC HYP, the last measurement prior to the first dose of DAC HYP will be used.

	Protocol 205MS303 Statistical Analysis Plan	Final Version 1.0
---	--	--------------------------

5.2.3. 205MS302-205MS303 Study Baselines

205MS303 Baseline

Study 205MS303 Baseline is defined as the latest available value prior to or on the date of the first dose of study treatment in Study 205MS303.

DAC HYP Baseline

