6.2. Demography and Baseline Disease Characteristics

6.2.1. Demography and Baseline Disease Characteristics for the 205MS301-303 ITT Population

Demographic data collected at the start of 205MS301 study (205MS301 Baseline) and at the start of 205MS303 study (205MS303 Baseline) for the 205MS301-303 ITT population will be summarized by previous 205MS301 treatment group and for all subjects combined. Demographic data will include age at baseline (years), age category (<18, 18-19, 20-29, 30-39, 40-49, 50-55, and >55, also ≤ 35 , >35), gender, height, race category and weight (kg).

Medical history (collected at the start of 205MS301 and updated since) will be summarized by prior treatment group in the 205MS301 study and for all subjects combined for the 205MS301-303 ITT population. Other baseline characteristic data at 205MS301 Baseline and at 205MS303 Baseline (e.g., EDSS test scores, the number of relapses in a year prior to baseline, MRI endpoints) will also be summarized for the 205MS301-303 ITT population using descriptive statistics by 205MS301 treatment group and for all subjects combined.

EDSS test score at the 205MS303 baseline is defined as score at the most recent assessment prior to the first dose in 205MS303, excluding assessments occurring within 29 days after a relapse onset.

The following MRI characteristics will be presented for the 205MS301 baseline and the 205MS303 baseline in the 205MS301-303 ITT population: the number of Gd lesions, the number and volume of T2 hyperintense lesions, and the number and volume of T1 hypointense lesions.

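### The 205MS303 baseline EDSS for the 205MS301-303 cohort is defined two ways, and the rule in the progression section lets a score taken during a relapse set the progression threshold

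*SAP*

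**What the plan says.** Three places in the SAP bear on the EDSS score that serves as 205MS303 baseline in the 205MS301-303 cohort.

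- **Section 5.2.1**, the general rule for any measurement: "the latest available value prior to or on the date of the first dose of study treatment in Study 205MS303". It mentions no relapse.
- **Section 6.2.1**, which defines the EDSS baseline by name: "EDSS test score at the 205MS303 baseline is defined as score at the most recent assessment prior to the first dose in 205MS303", and then adds "excluding assessments occurring within 29 days after a relapse onset".
- **Section 7.4.1**, the progression section: "For the 205MS303 baseline, the last available EDSS score before or on the first dose in the 205MS303 study will be used". Again there is no relapse exclusion.

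Section 7.4.1 ties the endpoint to this score: "For the 205MS303 Treatment Period, progression must start after the first dose in the 205MS303 study and will be calculated relative to 205MS303 baseline". The event is "at least a 1.0 point increase on the EDSS from baseline EDSS ≥ 1.0 that is sustained for 24 weeks", or 1.5 points from a baseline of 0. For the visits after baseline the section has a relapse safeguard: "Progression will not be confirmed at a visit where a relapse is also occurring". It counts a relapse as lasting at least 29 days from its start, which is the window used in 6.2.1.

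**The concern.** A subject assessed during a relapse shortly before the first 205MS303 dose can have two different baseline scores under the same plan. The baseline table would report one and the progression analysis would use the other. Nothing in the SAP limits the 6.2.1 definition to the baseline table, and nothing ranks the two rules.

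An EDSS raised by a relapse is a poor reference point for later worsening. If it becomes the baseline, the score needed for progression rises with it, and a subject who worsens durably from the pre-relapse level may not reach it, or may reach it later. If the unrestricted rule is also applied to EDSS change in Section 7.7.1, recovery from the relapse appears as improvement on treatment. The EDSS covariate in the 205MS303 relapse-rate model of Section 7.2.1, split at 2.5, refers to the same baseline and inherits the ambiguity.

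**Working it through.** The SAP states no figure that can be reproduced here: no relapse rate at entry, no expected number of progressions, no power. The check therefore compares the rules, applies the threshold under each, and sizes the exposed group under a stated assumption.

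**1. The rules compared**

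| Section | Score used as 205MS303 baseline | Relapse exclusion |
|---|---|---|
| 5.2.1 | latest value up to and including the day of first dose | none |
| 6.2.1 | most recent EDSS before first dose | assessments within 29 days after relapse onset left out |
| 7.4.1 | last EDSS up to and including the day of first dose | none |

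Sections 5.2.1 and 7.4.1 agree with each other and conflict with 6.2.1. The wording on scores from the day of first dose also differs. That matters little, because footnote 1 to Table 1 puts these assessments ahead of dosing.

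**2. Effect on the threshold**

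Formula from 7.4.1: threshold = baseline + 1.0 if baseline is at least 1.0; baseline + 1.5 if baseline is 0. Illustrative scores:

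| Pre-relapse EDSS | Last pre-dose EDSS, in relapse | Threshold, 6.2.1 rule | Threshold, 7.4.1 rule | Gap |
|---|---|---|---|---|
| 0 | 1.0 | 1.5 | 2.0 | 0.5 |
| 0 | 2.0 | 1.5 | 3.0 | 1.5 |
| 2.0 | 3.0 | 3.0 | 4.0 | 1.0 |
| 2.0 | 3.5 | 3.0 | 4.5 | 1.5 |
| 3.0 | 5.0 | 4.0 | 6.0 | 2.0 |

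From a pre-relapse score of 1.0 or more, the threshold rises by the full relapse increment. From 0 it rises by 0.5 less, because the required increase falls from 1.5 to 1.0. In the fourth row, a sustained score of 3.0 to 4.0 after entry is progression under 6.2.1 and not under 7.4.1. A score of 4.5 or more is progression under both, though possibly dated later under 7.4.1.

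**3. How many subjects are exposed**

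Inputs: window of 29 days (6.2.1); about 1200 subjects from 205MS301 (Section 2); relapse rate at entry r, assumed to be 0.1 to 0.5 per year. The share with a relapse onset in the 29 days before the last pre-dose EDSS, if visit timing is unrelated to relapse, is 1 − exp(−r × 29/365.25).

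| r per year | Share exposed | Of 1200 |
|---|---|---|
| 0.1 | 0.79% | 9.5 |
| 0.2 | 1.58% | 18.9 |
| 0.3 | 2.35% | 28.2 |
| 0.4 | 3.13% | 37.5 |
| 0.5 | 3.89% | 46.7 |

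EDSS visits prompted by a relapse would raise these shares somewhat.

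**4. Exposed is not reclassified**

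The result changes only for a subject whose later sustained score lies between the two thresholds, or crosses them at different dates. The SAP has no figure for that share. If it were 20% to 40% of those exposed (an assumption), the range is 0.79% × 0.20 = 0.16% to 3.89% × 0.40 = 1.56% of subjects, or about 2 to 19 of 1200.

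**5. What is outside the problem**

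Section 7.4.1 measures progression in the Combined Study Period from the 205MS301 baseline, so that analysis is untouched. For the 205MS203 and 205MS302 cohorts, Sections 6.2.2, 6.2.3, 7.4.2 and 7.4.3 state no relapse exclusion, so there is no conflict in those cohorts.

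**The case against.** **Baseline may differ by analysis.** Section 5.2 says that the definition depends on the analysis and the cohort, and the 7.4.1 sentence closes a paragraph on missing EDSS baselines, so it may have been meant as a fallback. This makes the intent unclear but does not reconcile the text. Section 6.2.1 defines the named quantity without limiting it to a table, and 7.4.1 gives its rule without calling it a fallback.

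**The exclusion has its own error.** This objection stands. With a pre-relapse baseline, incomplete recovery from a relapse that began before the first 205MS303 dose can count as progression in 205MS303. In the example starting from 2.0, a lasting 3.0 may be deficit already present at entry, although 7.4.1 requires progression to begin after the first dose. A reader might infer that every case lost under the 7.4.1 rule is true progression; the SAP does not support that.

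**The safeguard is narrow.** Section 7.4.1 bars confirmation during a relapse. It does not bar a relapse visit from starting a tentative progression, so the plan does not reject relapse scores altogether. That is correct, but a baseline fixes the reference for every later visit, and 6.2.1 already excludes such scores there.

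**Bias between prior-treatment groups.** A reader might infer that the group with more relapses at the end of 205MS301 is affected more, and that this flatters the switch to DAC HYP. The SAP gives no relapse rates by group at that time. Even with assumed rates of 0.2 and 0.4 per year, exposure would differ by 3.13 − 1.58 = 1.55 percentage points, and reclassification by less.

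**Importance.** Adverse events are the primary endpoints. Progression is secondary, analysed descriptively by Kaplan-Meier, and Section 7.4.1 specifies no between-group test. This lowers the severity.

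**Conclusion.** The contradiction is certain on the text, for the 205MS301-303 cohort. Its consequence is limited: in the 205MS303 Treatment Period, the 7.4.1 rule can cause progression to be missed or dated later in subjects whose last pre-dose EDSS falls within 29 days after a relapse onset. Recovery can appear as EDSS improvement only if the unrestricted rule is also used for EDSS change.

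About 1% to 4% of subjects are exposed, roughly 10 to 47 of 1200. This rests on an assumed relapse rate of 0.1 to 0.5 per year and on visit timing unrelated to relapse; the number reclassified would be smaller. The documents do not establish a difference in bias between prior-treatment groups. Severity is moderate: an inconsistent reference value for a secondary, descriptive endpoint, which should be settled before database lock so that the choice is not made with the results in view.

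**What to change.** State one 205MS303 EDSS baseline rule in Section 5.2 for the 205MS301-303 cohort: the last score on or before the first 205MS303 dose, leaving out assessments within 29 days after a relapse onset as 6.2.1 already does. Where no score qualifies, fall back on the last available score on or before first dose. Replace the separate wording in 6.2.1 and 7.4.1 with a reference to this rule, and refer to it in 7.2.1 (EDSS covariate) and 7.7.1 (EDSS change).

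Report how many subjects have different baselines under the two rules, by prior-treatment group. Repeat the 205MS303 Treatment Period progression analysis with the unrestricted baseline as a sensitivity analysis, because a pre-relapse baseline can count residual deficit from a pre-entry relapse as progression.

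Using the same rule in the other two cohorts is optional, for consistency; it corrects no contradiction there.

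The cost is a few sentences in the SAP, one count and one repeated analysis, with no new data. Some subjects will have an older baseline score. How much older cannot be read from the SAP, since the 205MS301 EDSS schedule is not shown and entry may follow completion of that study by up to 6 months.

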7.4.2. Sustained 6-month Disability Progression in the 205MS203-303 ITT Population

Time to confirmed 6-month disability progression will be summarized for the 205MS203-303 ITT population in the 205MS303 Treatment period. For the 205MS303 Treatment Period, progression will be calculated relative to the EDSS score at the 205MS303 baseline. Subjects who do not have a sustained progression will be censored on the date of the last EDSS prior to the end date of the 205MS303 treatment period. For subjects with a tentative progression that cannot be confirmed because there are no additional EDSS assessments, the follow-up ends before a sustained progression occurs (i.e., due to the subject withdrawing from the study or due to the cutoff of data collection), or because the confirmatory assessment does not meet other criteria (i.e., the last EDSS assessment is <158 days after the tentative progression or the last EDSS assessment is at the time of a relapse), the censor date will be the date of the last EDSS assessment. Due to the limited number of subjects, no imputation will be conducted for subjects with tentative progression in the 205MS203-303 ITT population.

Time to confirmed disability progression will be explored using Kaplan-Meier method, with the first dose date in the 205MS303 Treatment period as the start date for all subjects combined. Kaplan-Meier method for time to disability progression will be used to estimate the proportion of subjects who experienced progression at selected time points for all subjects combined.

	Protocol 205MS303 Statistical Analysis Plan	Final Version 1.0
---	--	--------------------------

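### The imputation model for unconfirmed last progressions is fitted to records selected by outcome, so its confirmation probability is too high whenever subjects have repeat tentative progressions

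*SAP*

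**What the plan says.** Section 7.4.1 defines confirmation episode by episode: a progression is confirmed when "this minimum EDSS change is present on the next study visit occurring after 158 days from the initial observation". In the main analysis, a subject whose tentative progression cannot be confirmed is censored: "the censor date will be the date of the last EDSS assessment".

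The sensitivity analysis replaces that censoring by imputation. It applies in this situation: "If a subject has a tentative progression at the last EDSS assessment and no EDSS assessments to confirm progression". The model is introduced as follows: "Among subjects with at least one tentative progression, the probability of confirmation for those with a missing EDSS to confirm progression will be estimated". It is a logistic regression on 205MS301 treatment group, baseline EDSS, "change in EDSS from baseline to the tentative progression and presence (or absence) of a relapse within the last 29-days of the tentative progression". Subjects with several tentative progressions contribute one record, namely "the confirmed (if subject had a confirmed progression) or the last (if subject did not have any tentative progressions confirmed) tentative progression record". The imputation is "conducted 50 times with pre-specified random seed to generate 50 analysis datasets".

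The analysis covers the 205MS301-303 cohort only. Section 7.4.2 states that "no imputation will be conducted for subjects with tentative progression in the 205MS203-303 ITT population", and section 7.4.3 says the same for the 205MS302-303 cohort.

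**The concern.** The unknown quantity is whether one particular episode, the one pending at the last EDSS, would have been confirmed. The model that supplies its probability is trained on records picked by looking at the outcome:

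- A subject with two failed episodes and then a confirmed one enters as a single success.
- A subject with three failed episodes enters as a single failure.
- A subject with two failed episodes and then a pending one keeps only the pending record, so the two observed failures are lost.

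Every record lost in this way is a failure. No covariate counts earlier failed episodes, and adjusting for the listed covariates cannot undo selection on the outcome.

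This is the only sensitivity analysis that section 7.4 describes for the progression endpoint. Section 2 records that the study was closed early, which can leave last episodes without a confirmatory visit. If the imputation itself is tilted upward, the gap between the main and sensitivity results mixes the effect of missing confirmation with an artefact of record selection.

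**Working it through.** **Inputs.** The selection rule, the covariates and the per-episode confirmation rule come from section 7.4.1. The SAP states no confirmation probability, no frequency of repeat episodes and no number of pending subjects, so there is no planned figure to reproduce. The following are assumptions:

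- p: probability that an evaluable tentative progression is confirmed.
- r: chance of a further tentative progression after a failed one.
- c: chance that an episode is unevaluable because follow-up ends, taken as random.

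**Closed form.** Let D = 1 − (1−c)(1−p)r.

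- A subject's retained record is a success with probability (1−c)p / D.
- It is an evaluable failure with probability (1−c)(1−p)(1−r) / D.
- The success rate among retained evaluable records is therefore p / [p + (1−p)(1−r)] = p / [1 − (1−p)r].

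The fraction c cancels. The relative error is 1/[1 − (1−p)r] − 1, which is zero only when r = 0 (or p = 1).

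| True p | r = 0 | r = 0.1 | r = 0.3 | r = 0.5 |
|---|---|---|---|---|
| 0.3 | 0.300 | 0.323 (+8%) | 0.380 (+27%) | 0.462 (+54%) |
| 0.4 | 0.400 | 0.426 (+6%) | 0.488 (+22%) | 0.571 (+43%) |
| 0.5 | 0.500 | 0.526 (+5%) | 0.588 (+18%) | 0.667 (+33%) |
| 0.7 | 0.700 | 0.722 (+3%) | 0.769 (+10%) | 0.824 (+18%) |

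Example: for p = 0.3 and r = 0.5, 0.3 / (1 − 0.7 × 0.5) = 0.3 / 0.65 = 0.462.

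**Check with the SAP's own covariates.** A simulation used 60,000 subjects with a tentative progression per setting, 20% of episodes unevaluable at random, and p = 0.3, 0.5 and 0.7. The four-covariate logistic model was fitted to the SAP's retained records, and its mean prediction for pending subjects was compared with their true probability. Without between-subject heterogeneity:

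| r | Subjects with more than one episode | Excess in imputed probability |
|---|---|---|
| 0 | none | about 0 points |
| 0.1 | 2.5-5.5% | about 2-3 points |
| 0.3 | 7-17% | about 7-9 points |
| 0.5 | 12-28% | about 12-17 points |

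With a random subject intercept (SD 1), the excess was about 2-3, 7-8 and 14-17 points for r = 0.1, 0.3 and 0.5.

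**Check of the repair.** The same model fitted to all evaluable episodes came within about 0.5 points of the truth in every setting. First episodes only came within about 0.5 points without heterogeneity and about 2 points with it. For p = 0.5, r = 0.3 and no heterogeneity: truth 0.500, SAP rule 0.590, all episodes 0.505, first episode 0.504.

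**Carry-through to the endpoint.** The excess applies only to pending subjects. If, as an assumption, 2-10% of the cohort are pending, an excess of 2-17 points moves the crude proportion progressing by roughly 0.02 × 2 = 0.04 to 0.10 × 17 = 1.7 percentage points.

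**The case against.** The strongest defence is that the target is the subject's status and not the episode's, since the SAP speaks of imputing presence or absence of sustained progression. Suppose a subject with a pending episode stayed in follow-up and could have further episodes. The probability P of ever confirming would satisfy P = p + (1−p)rP, so P = p / [1 − (1−p)r], exactly what the retained records estimate. The algebra stands, but the reading does not fit the text. The model concerns a missing EDSS that would have confirmed a progression, and two of its covariates describe that one episode. Section 7.4.1 also dates a progression from the visit where the change is first met, so confirmation from some later episode cannot be credited to the pending one.

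Three limits do stand. First, the size cannot be fixed from the SAP, and mild cases are possible. The EDSS schedule (Weeks 12 and 24, then every 24 weeks to Week 240) leaves room for repeats but says nothing about their frequency. Second, the upward direction assumes that pending episodes resemble evaluable ones given the covariates. If unresolved last episodes truly confirm more often, part of the excess would be offset, though the SAP does not argue this. Third, one record per subject does avoid within-subject correlation, which the repair must handle.

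A reader might infer that the comparison of former IFN β-1a and DAC HYP subjects is distorted. That would need repeat episodes to differ by group. For example, with p = 0.4 in both groups but r = 0.3 in one and 0.5 in the other, the rule gives 0.488 against 0.571. Nothing in the SAP indicates such a difference, so this remains hypothetical.

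**Conclusion.** The point holds for the section 7.4.1 sensitivity analysis in the 205MS301-303 cohort. Selecting records by outcome makes the imputed confirmation probability too high whenever some subjects have more than one tentative progression, provided that pending episodes resemble evaluable ones given the covariates.

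Under the assumed values, the relative error runs from zero (no repeats) through about 3-8% (r = 0.1, p from 0.3 to 0.7) to about 18-54% (r = 0.3 to 0.5, p from 0.3 to 0.5). At p = 0.7 the last range falls to 10-18%.

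It is tempting to read 18-54% as the error in the proportion progressing, or to conclude that the progression results as a whole are biased. The SAP supports neither. The figure concerns the imputation probability for pending subjects only, and the main Kaplan-Meier analysis censors those subjects without using the model. Section 5.4 describes the analyses as generally descriptive, and the primary endpoints are adverse events. The excess also adds progressions, so it cannot make long-term outcome look better in absolute terms. The change is worth making because it is cheap and this is the only check of its kind, but no main result depends on it.

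**What to change.** Replace the record-selection sentence in section 7.4.1. Fit the logistic model to all evaluable tentative progressions, confirmed or failed, including earlier failed episodes of subjects whose last episode is pending. Allow for clustering within subject, for example by drawing the model parameters for the 50 imputations from a cluster-robust covariance or by a subject-level bootstrap. Impute only the pending last episode.

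A simpler and slightly less accurate alternative is to fit the model to each subject's first evaluable tentative progression, whatever its outcome.

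The cost is one changed sentence, a changed selection step and a slightly more complex imputation step. No new data are needed.
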